VATS – Video Assisted Thoracoscopic Surgeries

CONFIDENTIAL

This material is the property of the University of Pennsylvania.

Study Summary

Title	Two-Part Study to Evaluate the Safety and Efficacy of Image Guided Surgery using Near-Infrared Dyes for Intramolecular Imaging of Nervous System Tumors Compared to Standard of Care, (TumorGlow™)
Short Title	Indocyanine Green for All Nervous System Tumors
Protocol/IRB Number	822231/UPCC #09315
Phase	Phase I/II
Methodology	Open Label; Part 1 observational and Part 2 permitting deviation from surgical plan based on indocyanine green intraoperative imaging.
Study Duration	5 years
Clinical Sites	Penn Medicine: Hospital of the University of Pennsylvania Penn Medicine Pennsylvania Hospital Penn Medicine Presbyterian Hospital
Objectives	
Part I: To determine safety/efficacy of high dose, delayed indocyanine green (second window ICG) during surgery of nervous system tumors.
 
Part II: To determine diagnostic test characteristics (sensitivity/specificity) of delayed, high dose indocyanine green (second window ICG) as a diagnostic aid during surgery of nervous system tumors.
 
Part IIb: To optimize timing and dose of second window IcG during surgery of nervous system tumors, based on sensitivity/specificity.
 
Part IIc: Compare SOC dyes with indocyanine green to determine efficacy for tumor visualization, answering the question is one dye superior to another, more accurate and precise.

Number of Subjects	We intend on enrolling 500 subjects in this study.
Diagnosis and Main Inclusion Criteria	Patients presenting with suspected resectable nervous system tumors who are considered to be good surgical candidates and are at risk of local recurrence.
Investigational Product, Dose, Route, Regimen	The study drug is indocyanine green, single dose of up to 5 mg/kg administered up to 72 hours prior to resection or a single dose of 25 mg administered during induction, diluted into sterile water for intravenous (IV) injection prior to tumor resection. Dye and dose plan is determined by PI based on tumor type, surgical timing, and signal to background ratio.
Investigational Devices	
 • VS₃ Iridium – Visionsense Stereoscopic High Definition (3DHD) including IR Fluorescence Vision System • Stryker 1588 AIM (Advanced Imaging Modality) Video Camera with Infrared Compatibility with Stryker AIM HD Autoclavable Laparoscope • Zeiss INFRARED™ 800 for OPMI® PENTERO® 800 • Leica FL800 ICG Fluorescence Module with the Leica M530

CONFIDENTIAL

This material is the property of the University of Pennsylvania.

	
OH6
 
• Surgical Dual Imager
Statistical Methodology	Statistical methodology includes analyses of sensitivity, specificity, and predictive value as they relate to indocyanine green-mediated tumor identification as compared to histopathology.

CONFIDENTIAL

This material is the property of the University of Pennsylvania.

1 Introduction

This study is conducted according to United States (US) and international standards of Good Clinical Practice (GCP) (Food and Drug Administration [FDA] Title 21 part 312 and International Conference on Harmonization [ICH] guidelines), applicable government regulations and institutional research policies and procedures.

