1.3 Name and Description of the Investigational Devices

Imaging Systems Intended for Use in the Neurosurgical Operating Room (OR):

Investigational Device	Manufacturer	FDA Product Classification / 510(k)	Use of Device (Visit 3: Operative Visit)	Hospital Used
VS ₃ Iridium – Visionsense Stereoscopic High Definition (3DHD) including IR Fluorescence Vision System	VisionSense (Medtronic)	Confocal Optical Imaging; Endoscope and accessories; Class II; VS3-IR 510(k): K152204	1) Dura View; 2) Cortex View; 3) Tumor View; 4) Margin View 5) Ex-vivo View	PAH; HUP
Stryker 1588 AIM (Advanced Imaging Modality) Video Camera with Infrared Compatibility with Stryker AIM HD Autoclavable Laparoscope	Stryker	Confocal Optical Imaging; Endoscope and accessories; Class II; VS3-IR 510(k): K173866	1) Dura View; 2) Cortex View; 3) Tumor View; 4) Margin View 5) Ex-vivo View	PPMC
INFRARED™ 800 for OPMI® PENTERO® 800	Carl Zeiss Surgical GMBH	System, X-Ray, Angiographic; Angiographic x-ray system; Class II; 510(k): K100468	Tumor View	PAH; HUP; PPMC
Leica FL800 ICG Fluorescence Module with the Leica M530 OH6	Leica Microsystems	System, X-Ray, Angiographic; Angiographic x-ray	Tumor View	PAH; HUP

CONFIDENTIAL

This material is the property of the University of Pennsylvania.

Investigational Device	Manufacturer	FDA Product Classification / 510(k)	Use of Device (Visit 3: Operative Visit)	Hospital Used
		system; Class II; 510(k): K141136		
Surgical Dual Imager	[name]	Confocal Optical Imaging; Endoscope and accessories; Class II; 510(k): Not Yet Approved	1) Tumor View 2) Margin View 3) Ex-vivo View	PAH

HUP = Hospital of the University of Pennsylvania; NIR = near-infrared; PAH = Pennsylvania Hospital; PPMC = Penn Presbyterian Medical Center

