1.6 Dose Rationale

In this study, the indocyanine green dose began at 5 mg/kg, aligned with previous nonclinical and clinical experience at the University of Pennsylvania. Given the incidence of HTN in our CNS cohort and seeking optimal signal to background ratio, we decreased to 2.5 mg/kg to assess efficacy and safety. Thus, we intend to evaluate dose ranges but will not exceed 5mg/kg. Alternately, based on neurosurgeon plan, patients may receive a 25 mg bolus of ICG at the time of induction administered intravenously by the anesthesiologist. This 25 mg dose of indocyanine green is similar to dosing for other intraoperative vascular visualization. This can cause less usage of the drug, lower risk of adverse event occurrences.

We make no changes to the route of administration.. The most important difference between what is labeled on the package and this protocol is the dose regimen (up to 5 mg/kg) and the amount of time elapsing before intraoperative imaging begins (up to 72 hours). This protocol began with 24-hour infusions the day before surgery based on previous nonclinical and clinical experience at the University of Pennsylvania. Interested in strength of signal to background ratio over extended or shortened timeframes, we allow for a range of up to 72 hours. The rationale for dosing timing prior to surgical intervention is based on the minimal risks with indocyanine exposure, to accommodate logistical scheduling of surgeries, and to collect data on optimal signal to background ratio in various tumor types.

Indocyanine green has been used in a dose-escalation trial up to a maximum dose of 10 mg/kg [\[22\]](#) and in other trials 3-5 mg/kg [\[13, 17-21\]](#). Indocyanine green has a LD₅₀ after IV administration of 50 to 75 mg/kg [\[22\]](#).

As [name] and other researchers have used an IV injection of indocyanine green to obtain imaging sufficient to describe discrepancies in the structure of abnormal hyper-vascularized tissue [\[47\]](#), it therefore stands to reason that we would be able to accomplish our objective of imaging tumors with indocyanine green using a similar dose.

CONFIDENTIAL

This material is the property of the University of Pennsylvania.

Interim data analysis (see [Section 7.2](#)), specifically the fluorescence signal to background ratio, will determine the optimal timing of indocyanine green infusion, which will guide future infusion in this protocol and future protocols.

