3.1 General Design

This study is a single center, open-label, two-part study to assess image guided surgery of intramolecular imaging in nervous system tumors. Subjects with a diagnosis of a resectable nervous system tumor who are at risk of recurrence are included. The primary goal is to observe what tissues fluoresce in the OR, and then to identify if that tissue is cancerous/tumor or normal when the histopathology is performed.

This study is split into two parts. The purpose of Part 1 is to confirm dose, assess timing of the operation and assess the feasibility of using indocyanine green as a fluorescent for neurosurgical tumor resection without extending surgery beyond what is seen on the standard of care MRI. The purpose of Part 2 is expansion of the margin view phase of the operation, where residual fluorescence can be resected at the discretion of the surgeon; in addition, further evaluation of optimal dosing and timing.

CONFIDENTIAL

Candidates are those with a presumed tumor in the nervous system that requires surgery. There is no randomization or control group.

Subjects undergo indocyanine green injection within 72 hours prior to surgery. Permitting infusion time within 72 hours of operation is believed to be adequate for tissue glow/surgical visualization. Alternately, patients may receive 25 mg of indocyanine green during induction. Dose and time of administration will be determined by the neurosurgeon during surgical planning. This 25 mg dose of indocyanine green is similar to dosing for other intraoperative vascular visualization.

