5.3 Method for Assigning Subjects to Treatment Groups

As this is an open-label study, there will be no randomization of treatment.

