7.2 Secondary Endpoints

For the secondary endpoint, we will use descriptive data on signal to background noise and safety data by tumor type to identify optimal dosing and timing of indocyanine green for intraoperative imaging in nervous system tumors. We will conduct an interim analysis after approximately 185 subjects are treated at the 2.5mg dose and 185 at the 5mg/kg dose.

Other important endpoints include safety and toxicity that includes review of vital signs and any reported or observed AE.

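### Section 7.2 seeks the optimal dose and timing from non-randomized data split only by tumor type, so the comparison may be confounded by period, infusion interval and possibly camera

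*Combined protocol and SAP*

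**What the plan says.** **Allocation.** Section 5.3 reads: "As this is an open-label study, there will be no randomization of treatment". The Study Summary gives the choice to the PI: "Dye and dose plan is determined by PI based on tumor type, surgical timing, and signal to background ratio". Section 3.1 gives it to the surgeon: "Dose and time of administration will be determined by the neurosurgeon during surgical planning".

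**Change over time.** Section 1.6 says: "In this study, the indocyanine green dose began at 5 mg/kg, aligned with previous nonclinical and clinical experience at the University of Pennsylvania". It continues: "Given the incidence of HTN in our CNS cohort and seeking optimal signal to background ratio, we decreased to 2.5 mg/kg". The same section says that infusion was first given the day before surgery and that the window was then opened to 72 hours, partly for scheduling and partly to study the ratio.

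**Imaging systems.** The device table in Section 1.3 lists VS3 Iridium for PAH and HUP, Stryker 1588 for PPMC, and the Surgical Dual Imager for PAH only. The Zeiss microscope is listed for all three hospitals and the Leica for PAH and HUP.

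**Analysis.** Section 7.2: "we will use descriptive data on signal to background noise and safety data by tumor type to identify optimal dosing and timing". It sets an interim analysis at about 185 patients per dose. Section 7.4 adds means, standard deviations, proportions and graphics. No section mentions adjustment or stratification for camera, hospital, period or study part, or for dose and interval against each other.

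**Use.** Section 1.6 says that the ratio at the interim analysis will settle the optimal timing, and that this will steer later infusions in this protocol and in others.

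**The concern.** Patients at the two doses differ in more than dose. They were treated in different stretches of the study, possibly at different infusion-to-imaging intervals, and possibly under different cameras. Clinicians chose the regimen partly on tumor type and on the ratios seen in earlier patients. A tabulation by tumor type removes one of these differences and leaves the rest.

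The result is meant to be acted on. A timing contrast that really reflects era, dose or camera would be read as a timing effect and would shape later infusions. A dose contrast with the same fault would go into the secondary endpoint as evidence of an optimal dose, and into the planning of the randomized study that Section 7.3 has in view.

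**Working it through.** **Inputs**
- Section 1.5, as of January 2019: 110 patients infused at 2.5 mg/kg and 186 at 5 mg/kg. 110 + 186 = 296, which matches the stated total. Part 2 had begun by then.
- Section 7.2: interim at about 185 per dose. The lower dose is printed there without the per-kilogram unit; it is read here as 2.5 mg/kg.
- Section 7.3 states that there is no sample size calculation, so nothing lies behind the 185 that could be reproduced.
- Effects of period and camera on the ratio: not in the documents, so assumed below.

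**1. Period imbalance, from the protocol's own counts**
- Still needed at 2.5 mg/kg: 185 − 110 = 75.
- Share of that interim group treated after January 2019: at least 75/185 = 41%.
- Still needed at 5 mg/kg: 185 − 186 = −1, so none. If the first 185 are used, the matching share is 0%.

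The imbalance is then 41 percentage points. It shrinks if patients treated at 5 mg/kg after January 2019 are also included.

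**2. What that imbalance could do (assumed effects)**

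Bias = period effect (in SD) × imbalance. SE = √(1/185 + 1/185) = 0.104 SD, so the 95% half-width is 1.96 × 0.104 = 0.20 SD. The last column assumes a two-sided 5% z-test and no true dose difference; the plan itself specifies no test.

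| Assumed period effect | Bias | False-positive rate |
|---|---|---|
| 0 | 0 | 5% |
| 0.25 SD | 0.25 × 0.41 = 0.10 SD | about 16% |
| 0.5 SD | 0.5 × 0.41 = 0.20 SD | about 50% |

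At the upper value the bias equals the sampling half-width.

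**3. Camera (both inputs assumed)**

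If cameras differ by a factor r in signal-to-background, and the share of patients on one camera differs by d between doses, the spurious difference in geometric-mean ratio is exp(d × ln r) − 1.

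| d | r = 1.3 | r = 2.0 |
|---|---|---|
| 0 | 0% | 0% |
| 0.2 | 5.4% | 14.9% |
| 0.4 | 11.1% | 32.0% |

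The documents give neither r nor d.

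**4. Interval**

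The documents give no cross-tabulation of dose by infusion-to-imaging interval. Section 1.6 shows that both changed during the study, so they may have moved together. A table of dose alone, or of timing alone, cannot separate them.

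**The case against.** The best defense is that the plan makes modest claims. Section 7.4 calls the analyses primarily descriptive, Section 7.3 says the study is to inform a later randomized trial, and this is a secondary endpoint in a non-randomized Phase I/II study. Section 7.2 also weighs safety data and does separate tumor types. All of that stands, and it limits the severity. It does not remove the point, because the section still sets out to identify an optimum and Section 1.6 has the timing result steer later infusions.

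Some stronger readings are tempting, but the documents do not support them:
- *That camera does confound the dose comparison.* This needs a dose mix that differs by hospital or camera, and no such counts are given.
- *That a patient's own ratio set that patient's dose.* Section 6.3 has the ratio read in the operating room; for pre-operative infusion that is after dosing. Only ratios from earlier patients can have steered later choices.
- *That each hospital has a single camera for margin imaging.* Section 1.3 also lists the Surgical Dual Imager for the margin view at PAH.
- *That an interim dose result is carried into later infusions.* Section 1.6 says this of timing.

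A further objection is that regression cannot separate dose from period if one dose simply replaced the other. That is correct: adjustment for period works only where the doses overlap in time, and the documents do not say how far they do.

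Extending the same model to adverse events would also go too far. Section 1.7.1 reports events in only 35 patients, and the main categories are infusion-type reactions, which for pre-operative infusion arise before any camera is used.

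**Conclusion.** The concern holds as a risk of confounding, not as a demonstrated bias. Followed as written, Section 7.2 has no means of telling a dose or timing effect from period, from the other of the two factors, or from camera.

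The period imbalance is the firmest part: at least about 41% of the 2.5 mg/kg interim group falls after January 2019, against possibly none of the 5 mg/kg group. This assumes that the interim takes about 185 per dose and that the first 185 at 5 mg/kg are used. The size of any resulting bias cannot be derived from the documents. It is zero if period has no effect on the ratio, and 0.10 to 0.20 SD under assumed effects of 0.25 to 0.5 SD. The camera component is conditional on an imbalance that is not shown, and is zero without one.

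The plan should be changed, because the timing result is to guide infusions within this same protocol.

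**What to change.** In Section 7.2:
1. Replace the crude tabulation with a regression of log signal-to-background on dose group and infusion-to-imaging interval together, adjusted for tumor type and camera/hospital. Use patient-clustered errors if a patient contributes several readings.
2. Add calendar period or study part to the model where the doses overlap in time.
3. Tabulate dose and interval by camera and by period, so that the overlap is visible.
4. Where there is no overlap, report the contrast as exploratory and do not call a regimen optimal.
5. Keep adverse events descriptive, by dose and period, without camera or imaging interval as covariates.

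The Study Summary and Section 3.1 should also be reconciled on who determines dose and timing, since the basis for that choice bears on what the analysis must adjust for.

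**Cost.** A little more analysis, and no new patients or procedures. The covariates should be recoverable from study records, but the case report forms are attachments not reproduced in the document, so this needs confirming. Intervals will be wider, possibly much wider for the period-adjusted dose contrast.

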1.1 Background

Primary malignant and non-malignant brain tumors account for an estimated 21.42 cases per 100,000 for a total count of 343,175 incident tumors based on worldwide population estimates [1]. These entities result in variable but disappointing rates of survival, particularly for primary brain tumors (5-year survival rates: anaplastic astrocytoma 27%; glioblastoma multiforme 5%) [2, 3]. Metastatic brain tumors outnumber primary brain tumors (estimates as high as 10:1) as they affect approximately 25% of patients diagnosed with cancer [4-6]. In terms of brain tumor surgery, the extent of surgical resection—a factor that is greatly impacted by a Neurosurgeon’s ability to visualize these tumors—is directly associated with patient outcomes and survival [7-9]. Although spinal cord tumors are lower in terms of their incidence [10], data correlating extent-of-resection to outcomes and survival have been demonstrated in patients with intramedullary tumors [11].

Using systemically delivered compounds with a high sensitivity of detection by near-infrared (NIR) fluorescence, it would be possible for us to improve surgical resection thus minimizing chances of recurrence and improving survival. Simply, if the tumor cells will “glow” during surgery, the surgeons are more likely to identify tumor margins and residual disease, and are, therefore more likely to perform a superior cancer operation. By ensuring a negative margin through NIR imagery, it would make it possible to decrease the rates of recurrence and thus improve overall survival.

This concept of intraoperative molecular imaging requires two innovations:

- (i) a fluorescent contrast agent that can be injected systemically into the subject and that selectively accumulates in the tumor tissues, and
- (ii) an imaging system that can detect and quantify the contrast agent in the tumor tissues.[12, 13]

[figure not shown]
Subjects undergo intraoperative imaging, receiving an injection of indocyanine green and then undergoing intraoperative imaging of the surgery site with a NIR imaging system. The imaging devices allow the operating field to be observed in real-time.

1.2 Name and Description of the Investigational Product

Indocyanine green is a water-soluble tricarbocyanine dye routinely used in clinical settings for measuring cardiac output, hepatic function, liver blood flow and ophthalmic angiography and has been in use for over 60 years [14]. This protocol utilizes Patheon’s indocyanine green, NDC 17238-424. The chemical formula is

CONFIDENTIAL

$C_{45}H_{47}N_2O_6S_2Na$ and the compound has a molecular weight of 774.96Da (CAS number 3599-32-4). It has a peak absorption in the NIR spectrum at 800nm and maximal emission at 835nm. Indocyanine green is rapidly and completely bound to plasma proteins (especially albumin) after intravenous (IV) injection in the blood [15].

Indocyanine Green for Injection USP is a sterile, lyophilized green powder containing 25 mg of indocyanine green with no more than 5% sodium iodide. It is packaged with Sterile Water for Injection, USP, which is used to dissolve the indocyanine green, and is to be administered intravenously.

1.3 Name and Description of the Investigational Devices

Imaging Systems Intended for Use in the Neurosurgical Operating Room (OR):

Investigational Device	Manufacturer	FDA Product Classification / 510(k)	Use of Device (Visit 3: Operative Visit)	Hospital Used
VS ₃ Iridium – Visionsense Stereoscopic High Definition (3DHD) including IR Fluorescence Vision System	VisionSense (Medtronic)	Confocal Optical Imaging; Endoscope and accessories; Class II; VS3-IR 510(k): K152204	1) Dura View; 2) Cortex View; 3) Tumor View; 4) Margin View 5) Ex-vivo View	PAH; HUP
Stryker 1588 AIM (Advanced Imaging Modality) Video Camera with Infrared Compatibility with Stryker AIM HD Autoclavable Laparoscope	Stryker	Confocal Optical Imaging; Endoscope and accessories; Class II; VS3-IR 510(k): K173866	1) Dura View; 2) Cortex View; 3) Tumor View; 4) Margin View 5) Ex-vivo View	PPMC
INFRARED™ 800 for OPMI® PENTERO® 800	Carl Zeiss Surgical GMBH	System, X-Ray, Angiographic; Angiographic x-ray system; Class II; 510(k): K100468	Tumor View	PAH; HUP; PPMC
Leica FL800 ICG Fluorescence Module with the Leica M530 OH6	Leica Microsystems	System, X-Ray, Angiographic; Angiographic x-ray	Tumor View	PAH; HUP

CONFIDENTIAL

This material is the property of the University of Pennsylvania.

Investigational Device	Manufacturer	FDA Product Classification / 510(k)	Use of Device (Visit 3: Operative Visit)	Hospital Used
		system; Class II; 510(k): K141136		
Surgical Dual Imager	[name]	Confocal Optical Imaging; Endoscope and accessories; Class II; 510(k): Not Yet Approved	1) Tumor View 2) Margin View 3) Ex-vivo View	PAH

HUP = Hospital of the University of Pennsylvania; NIR = near-infrared; PAH = Pennsylvania Hospital; PPMC = Penn Presbyterian Medical Center

1.4 Preclinical Data

The use of indocyanine green for imaging has been well-documented over the last 20 years. It is believed that indocyanine green, which is normally cleared quickly in vivo, gets “stuck” in tumors. The University of Pennsylvania laboratories have shown that indocyanine green can be used to safely and accurately image lung, breast, renal and ovarian cancers in mice and dogs. Work done at the Hospital of the University of Pennsylvania (HUP) in the lab of [name] has shown 5 mg/kg (given to mice in his lab) is an optimal dose for tumor imaging [25, 28]. In addition, performing optical imaging within 72 hours following dosing of indocyanine green is optimal based on Penn’s experience [25]. The LD₅₀ after IV administration ranges between 60 and 80 mg/kg in mice, 50 and 70 mg/kg in rats and 50 and 80 mg/kg in rabbits [16, 22].

Studies in a rat glioma model demonstrated that indocyanine green remained within tumors with relatively few glioma cells seen beyond the indocyanine green-laden tumor margin. The doses utilized ranged from 60 to 120 mg/kg with imaging taking place at least 1 hour following the dose [22]. In [name] lab, indocyanine green-injection utilizing canine tumor models demonstrated reliable uptake into flank tumor xenografts with visualization of the tumor/normal tissue interface [23-25].

